2.7.3 Interim Analyses and Data Monitoring

A DMC, guided by a charter, will review safety data during the enrollment and treatment phases of this study. The DMC will advise the Sponsor regarding the continuing safety of trial subjects and those yet to be recruited to the trial, as well as the continuing validity and scientific merit of the trial. The DMC is not charged with stopping the trial early for efficacy.

The primary analysis is planned when the last subject randomized and treated has completed the week 24 visit. The trial will remain blinded until the last subject has completed the Week 24 visit.

The final analysis will be repeated when the final subject has completed the Week 56 visit. A comparison of the Week 24 and Week 56 analyses will be performed to identify any changes in the database that occurred between unblinding and the final analysis.

[figure not shown]
2.7.4 Multicenter Studies

Data from all sites will be pooled for presentation.

2.7.5 Multiple Comparisons/Multiplicity

A serial procedure will be used to account for multiplicity of dose level for the primary endpoint and the secondary endpoints. This procedure will start with the 300 mg vs placebo comparison for the primary endpoint. If this is significant, testing will continue to a subset of the key secondary endpoints for 300 mg (first the Weeks 1-4 75% responder endpoint, then the Weeks 1-12 75% responder endpoint, and then the Weeks 1-12 50% responder endpoint). The procedure will then move on to the primary endpoint for the 100 mg group and subsequently to the same subset of key secondary endpoints as tested for the 300 mg dose. The procedure will then move on to the remaining key secondary endpoint for 300 mg and 100 mg (i.e., percentage of subjects with a migraine on the day after dosing). Only if all of these secondary endpoints reach statistical significance will the 30 mg group be tested.

Statistical testing will be conducted at the 5% alpha level.

3 STATISTICAL SUMMARIES

3.1 General Conventions

Unless otherwise stated, summary statistics including the number of subjects (n), mean, standard deviation, median, minimum and maximum will be presented for continuous variables. Generally the minimum and maximum values will be presented to the same decimal precision as the raw values, the mean and median values to one more, and the standard deviation, to two more decimal places than the raw values. This decimal place convention may be followed for all data elements. For categorical variables, per category, the absolute counts (n) and percentages (%) of subjects with data, and if appropriate, the number of subjects with missing data, will be presented. Percentages will be presented to one decimal place.

For PK data the following applies:

Concentration values for free ALD403 will be presented as received from the Bioanalytical Laboratory.

Values for all PK parameters and for mean concentrations will be presented in three or four significant digits, as appropriate, i.e., 3 significant digits for minimum and maximum, 4 significant digits for mean, SD and median; % CV is given to 1 decimal point.

For AEs, medical history and concomitant medications reported on a per-subject basis, the denominator for the percentage calculation will be the number of subjects at risk in each treatment group. A subject will be considered at risk if the subject is in the analysis set and in the subgroup of interest.

All p-values will be rounded to 4 decimal places. If a p-value is less than 0.0001 it will be displayed as "< 0.0001".

Unless otherwise specified all summaries will be performed by treatment group, all efficacy analyses will be based upon the full analysis population, all safety as well as demographic and baseline characteristic analyses will be based upon the safety population and all PK analyses will be based upon the PK population.

3.2 Definition of Baseline

Baseline assessment for migraine and headache endpoints will be based upon the data recorded in the headache eDiary during the 28 days following screening. For other variables, the baseline assessment will be the latest available valid measurement taken prior to the administration of Investigational Product. This will generally be Day 0.

3.3 Clinical Trial Subjects

3.3.1 Subject Disposition

The number of subjects signed informed consent, randomized, treated, discontinued Investigational Product early, and terminated from the clinical trial early will be summarized. The reason for early termination of Investigational Product or from the clinical trial will be summarized. Additionally, the summary of subjects present at each visit will be summarized. Subjects randomized but not included in the full analysis population and the reasons for exclusion will be summarized. The number of subjects screened and summary of screen failure reasons will also be summarized.

A listing of entry criteria that were not met will be produced.

3.3.2 Analysis Population

The number of subjects in each analysis population will be summarized.

3.3.3 Demographics and Baseline Characteristics

Demographic and baseline characteristics will be summarized descriptively by treatment group.

3.3.4 Prior and Concomitant Medications

Medications with a stop date before the treatment dosing date will be considered prior medications. Medications with a start or stop date on or after the treatment dosing date will be considered concomitant medications. All medications marked as ongoing are concomitant medications.

A medication with an incomplete stop date will be considered concomitant if:

- Month is missing and year is equal to or after the year of treatment dosing date
- Day is missing and year is equal to the year of the treatment dosing date and month is equal to or after the month of the treatment dosing date.

Concomitant medications will be summarized by treatment group. All medications will be provided in a listing.

Prophylactic and acute headache medications, identified by a clinical review of the coded concomitant medications data, will be summarized by treatment group.

The headache medications recorded in the eDiary will not be integrated with the concomitant medications as these two data capture tools have distinctly different format, purpose and functionality. These diary-based results will be summarized in a separate series of outputs. For these the percent of days that subjects used headache medication within each 4 week interval and in the trial as a whole will be summarized by treatment group. These summary measures will only include subjects who have completed the eDiary at least 21 days of the 28 days for the selected interval. In addition to the overall summary, descriptive statistics will be provided for each type of medication: Ergotamine, Triptan, Simple Analgesic, Opioid, Combination Analgesic and Other.

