2.7.2 Handling of Dropouts or Missing Data

Summary statistics will be reported based upon observed data except for the diary data, which will utilize the imputation outlined below. Additionally, if the start date of an AE or concomitant medication is incomplete or missing, it will be assumed to have occurred on or after the intake of trial medication, except if an incomplete date (e.g., month and year) clearly indicates that the event started prior to treatment.

Subjects who do not complete the eDiary daily will have missing data. It is expected that most missing diary data will be sporadic.

Missing Headache End Date and Time

If the end date and time for a headache recorded in the eDiary is missing the headache end date will be set to the earlier of 23:59 on the day before the next reported headache or 23:59 on the last entry reported into the diary (i.e. the last evening report or if no evening report was completed after the start of the headache 23:59 on the day the headache started). Headaches that are not reported as stopped by the subject are missing the answers to the questions that allow for the determination of whether the headache was a migraine or not. In this population most headaches are migraines. Hence, these headaches with missing 'end' information will be classified as migraines.

Missing Data Rule 1

If the eDiary has been completed at least 21 days in a 28 day interval, then a normalization procedure will be used. The results will be normalized to 28 days by multiplying the observed results by the inverse of the completion rate (e.g. if a subject does not complete the eDiary on 5 days they will have completed the diary on 82% of the days and the normalized results will be the observed results times 1.22).

Missing Data Rule 2

If the eDiary has been completed on less than 21 days in the 28 day interval then the results for the 28 day interval will be a weighted function of the observed data for the current four week interval and the results from the previous interval. The weights will be proportional to how many days the diary was completed and will provide greater weight for higher completion rates. Specifically, the results will be derived as

$$28 (W X_c + (1 - W) X_p),$$

where W is the number of days the diary was completed/20, X_c is the available average daily results for the current interval and X_p are the average imputed daily results for the previous interval.

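### The SAP's day-missing stop-date rule stops at the end of the dosing year, so a small group of drugs started before dosing and stopped in a later year can be left out of the concomitant medication table

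*SAP*

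**What the plan says.** All the classification rules are in SAP 3.3.4, Prior and Concomitant Medications.

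- Prior: "Medications with a stop date before the treatment dosing date will be considered prior medications".
- Concomitant: "Medications with a start or stop date on or after the treatment dosing date will be considered concomitant medications".
- Ongoing: "All medications marked as ongoing are concomitant medications".
- Incomplete stop date, month missing: concomitant if "Month is missing and year is equal to or after the year of treatment dosing date".
- Incomplete stop date, day missing: concomitant if "Day is missing and year is equal to the year of the treatment dosing date"; in addition, the stop month may not be earlier than the dosing month.

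The same section builds the prophylactic and acute headache medication summary from these data: the drugs are "identified by a clinical review of the coded concomitant medications data, will be summarized by treatment group". It also lists all medications whatever their class, and it keeps headache medication recorded in the eDiary in separate outputs.

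For an incomplete or missing start date, SAP 2.7.2 says that "it will be assumed to have occurred on or after the intake of trial medication", unless the partial date clearly shows an earlier start.

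**The concern.** The two bullets for incomplete stop dates do not match. The month-missing bullet reaches forward into later years; the day-missing bullet does not. The better-documented record can therefore be treated worse than the vaguer one. With a first dose in November 2016, a drug started earlier and recorded as stopped in February 2017 (day unknown) fails, while the same drug recorded only as stopped in 2017 passes.

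At stake is the completeness of a descriptive table. The concomitant medication summary, and the headache medication summary drawn from it, show what background treatment each arm received. A drug taken for about three months on study should appear there. Pre-dose starts are expected in this trial: Protocol 8.1 requires hormonal therapy to be stable for at least 3 months before screening, and Protocol 9.4 requires permitted barbiturates and prescription opiates to have been on a stable regimen for at least 2 months before screening.

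**Working it through.** The plan states no figure for this rule, so there is nothing to reproduce. The check applies the rules literally, then looks at how much of follow-up lies where the gap is.

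**Step 1. The rules applied to one case.** Take a hypothetical first dose on 15 October 2016 and a drug started before that date and not marked ongoing. Since the start is pre-dose, only the stop date can make the drug concomitant.

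| Stop date as recorded | Bullets as written | Corrected day-missing bullet |
|---|---|---|
| Sep 2016, day missing | not concomitant | not concomitant |
| Oct 2016, day missing | concomitant | concomitant |
| Dec 2016, day missing | concomitant | concomitant |
| Jan 2017, day missing | **not concomitant** | concomitant |
| Feb 2017, day missing | **not concomitant** | concomitant |
| Nov 2017, day missing | **not concomitant** | concomitant |
| 2016 only | concomitant | concomitant |
| 2017 only | concomitant | concomitant |

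The corrected bullet compares the pair (stop year, stop month) with (dosing year, dosing month). It changes only the three later-year rows. The November 2017 row passes the month test and fails on the year alone.

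If the drug started on or after dosing, every row is concomitant through the start-date rule.

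**Step 2. Who is exposed.** A record falls into the gap only if all four conditions hold:

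1. it started before dosing;
2. it is not marked ongoing;
3. its stop date has a known month and a missing day;
4. it stopped in a calendar year after the dosing year.

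**Step 3. Whether another rule closes the gap.** SAP 2.7.2 deals with start dates. SAP 3.6.1 sets an adverse event end date with a missing day to the last day of the month, which would classify these drugs correctly, but it applies only to the treatment-emergent adverse event tables.

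**Step 4. How much of follow-up lies in a later year.** Follow-up to Week 56 is 392 days (Protocol section 2; SAP Table 1), and Protocol 9.4 records medications through Week 56. Assume first doses spread evenly over a 365-day year, and let u = 0 to 364 be the day of the year of the first dose.

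- Week 56: days in a later year = 392 − (365 − u) = 27 + u. The mean is 27 + 182 = 209, and 209/392 = 53%. The minimum is 27/392 = 7%; the maximum is 391/392, nearly 100%. Every subject who completes crosses a year-end.
- Week 24: days in a later year = max(0, 168 − (365 − u)) = max(0, u − 197). The sum over u is 1 + 2 + … + 167 = 14,028. The mean is 14,028/365 = 38.4 days, and 38.4/168 = 23% (range 0% to 167/168 = 99%).

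These are shares of days. Turning them into a count of records would need the proportion of stop dates with a missing day, which the documents do not give.

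**The case against.** The best defence is that the general sentence already covers these drugs. A stop in February 2017 is after a November 2016 dose whatever the day, and the SAP says that an incomplete date counts *if* a bullet is met, not *only if*. This is a possible reading, but it does not remove the problem. The month-missing bullet spells out later years, so the authors evidently thought that case needed stating, and a programmer who codes the second bullet as written will exclude these records. At best the general sentence and the specific bullet conflict.

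Several other points on that side do stand.

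- A reader might infer that drugs continued into the following year generally disappear from the tables. They do not: failing any one of the four conditions in Step 2 keeps the record in.
- A reader might infer that the affected drugs are labelled prior. They are not: the prior definition needs a stop before dosing, so they are left unclassified.
- A reader might fear for the prophylactic summary. Regular prophylactic use was barred from 2 months before screening to randomization (Protocol 8.1), and prophylactics were prohibited through Week 24 (Protocol 9.4). Prophylaxis begun after dosing is caught by its start date. What can be lost is permitted short-term use and breaches of the entry criteria.
- Acute headache medication use is also summarized from the eDiary, which does not use this rule.
- The rule does not depend on treatment arm, and nothing in the documents suggests that the loss would differ between arms.

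**Conclusion.** The day-missing bullet is wrong as written and inconsistent with its neighbour. Its literal effect is to leave unclassified a narrow set of drugs that were plainly taken on study. The consequence is limited to a descriptive concomitant medication table and, for the few such records, the headache medication table derived from it. The listing is complete, and no efficacy endpoint depends on the rule. This is a minor correction, worth making but not urgent.

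The 53% and 23% rest on evenly spread dosing dates and describe only the opportunity for a later-year stop. They should not be read as the share of medications lost, which is unknown and, with medications reviewed at every visit, may be small.

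**What to change.** Reword the second bullet of SAP 3.3.4 so that a stop date with a missing day is concomitant when either the stop year is later than the dosing year, or the stop year is the dosing year and the stop month is the dosing month or later.

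Inserting a reference to later years in the existing year test would not be enough. The month test would still apply, and a January or February stop after an October dose would still fail. The comparison has to be on year and month together.

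The cost is one clause in the SAP and one line of code. In the cases checked above it changes only the later-year, day-missing records, and there is no evident downside.

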3.3.5 Medical History

Medical History will be tabulated by system organ class, preferred terms and treatment groups.

For females, menstrual medical history will be summarized by treatment groups.

Migraine History including age at diagnosis, the average number of headache days, migraine days, and migraine attacks per 28 day period in the 3 months prior to screening, as well as the timing of the start of migraines in relation to puberty/ menarche and hormone migraine history for females will be summarized in a table by treatment groups.

3.3.6 Clinical Trial Treatment

Total volume infused and reason for dose interruption will be listed as well as summarized in a table.

3.3.7 eDiary Compliance

The rate of missing eDiary data within each four week interval, which is defined as (number of days with missing eDiary data / 28) * 100, will be summarized descriptively. A day will be considered as missing if the subject did not interact with their eDiary and the subject did not experience a headache on that day.

3.4 Analysis of Efficacy Endpoints

3.4.1 Headache/Migraine Days and Acute Migraine Medication Days

Summary tables for the number of migraine/headache days, change from baseline and the percent change by 4, 12 and 24 week intervals and treatment group will be produced. Similar tables will be produced for acute migraine medication days and the change from baseline acute migraine medication days. The treatment difference and associated confidence interval will also be provided. These confidence intervals will be based on normal approximation. Stratification will not be used for these intervals.

Additionally, the SAS procedure, Proc Mixed using the ANCOVA model controlling for the effects of baseline migraine days outlined in Section 2.5, will be used to calculate the estimated treatment difference from placebo, the change from baseline and the associated confidence intervals for Weeks 1-12. The ANCOVA model will also be used to test for a treatment difference in the primary endpoint change from baseline in migraine days for Weeks 1-12 and for the change from baseline days of acute migraine medication use for Weeks 1-12. Significant p-values based on the formal decision rule criteria outlined in Section 2.7.5 will be clearly noted.

Plots of the migraine days and change from baseline and for days of acute migraine medication use and change from baseline will be produced. These plots will use the four week intervals as

the X-axis. A separate set of graphs that provide histograms of the Week 1 to 12 results for these three parameters will also be produced.

The change from baseline in migraine days for the six, 4 week intervals from Weeks 1 to 24 will also be analyzed using repeated measures. The model will include treatment group, timepoint (Weeks 1-4, 5-8 9-12, 13-16, 17-20, 21-24), and baseline migraine days as fixed factors. Estimated treatment difference, for each timepoint, and associated confidence interval will be estimated using SAS procedure, Proc Mixed. The unstructured (UN) covariance structure will be specified. If the model fails to converge, an alternative covariance structure will be specified. The timepoint variable will be categorical and baseline migraine days will be continuous. The repeated measures analysis will be repeated for weeks 1-12 using the same subjects and a subset where only subjects/four week intervals where the eDiary was completed a minimum of 21 days and applying Missing Data Rule 1 described in Section 2.2.2. Only the overall week 1-12 estimated treatment difference, associated confidence interval and p-value will be reported for this analysis.

The change from baseline in migraine days for Weeks 1-12 will be summarized within the subgroups outlined in Section 2.7.1 forest plot of the treatment difference and associated confidence interval will also be presented.

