2.5 Statistical Assessment of the Trial Objectives

Hypothesis testing will be performed for the primary endpoint: change from baseline in migraine days from Weeks 1-12. This endpoint will be calculated as outlined in Section 2.2.2 and will utilize the missing data rules provided in Section 2.7.2. The hypotheses tested are

$$H_o: \Delta_{plb} = \Delta_{403} H_a: \Delta_{plb} \neq \Delta_{403}$$

where Δ_{403} is the change in migraine days for subjects in the ALD403 treatment arm and Δ_{plb} is similarly defined for the placebo subjects. The change from baseline is expected to be negative as migraines are being reduced. While the test outlined above is two sided, as is the alpha level used for this study (i.e. 5%), clinically relevant results require a larger reduction of migraines on the ALD403 arms.

An ANCOVA model will be used to test for a difference between treatment arms. This model will include the change from baseline measure as the response variable. Treatment and the stratification variable: baseline migraine days (continuous covariate) will be the independent variables.

In addition, model based estimates including confidence intervals for the treatment differences will be used to summarize the results for the primary endpoint.

A sensitivity analysis of the change from baseline in migraine days will be performed using the sensitivity missing data rule provided in Section 2.7.2.

Secondary Efficacy Analyses

Summary statistics including confidence interval for the treatment differences will be used to summarize the results for the secondary endpoints. Testing will be performed for the key secondary endpoints and for the change in acute migraine medication days endpoint. For the key secondary endpoints (responder rates and percentage of subjects with a migraine on the day after dosing) this testing will utilize a CMH/extended CMH test. The tests will be stratified by the randomization stratification factor. The change in acute migraine medication day endpoints will be tested using an ANCOVA model similar to the one used for the primary endpoints: change from baseline measure as the response, treatment and baseline acute migraine medication days as independent variables. The time to first migraine analysis will be descriptively summarized based upon Kaplan-Meier methods.

Exploratory Analyses

Exploratory endpoints will be summarized with descriptive statistics by treatment group.

20

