2.7 Statistical/Analytical Issues

2.7.1 Adjustments for Covariates and Examination of Subgroup Analyses

Summaries with descriptive statistics and frequency counts for change in migraine days will be provided for the subgroups indicated below. A forest plot will also be created for subgroup analyses and will display treatment differences. The subgroups will be

- Calculated baseline migraine days (<9 days vs. ≥9 days)
- Sex
- Race (White, Black or African American, Other)
- Age Group (\leq 35 yrs, \geq 35 yrs)
- Age Group at Diagnosis of Migraine (≤21 yrs, >21 yrs)
- Duration of Migraine at Baseline (≤15 yrs, >15 yrs)

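### SAP 3.4.1 leaves most descriptive change-from-baseline intervals unadjusted for baseline; extending the planned ANCOVA to them is a free gain in precision

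*SAP*

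**What the plan says.** SAP 3.4.1 plans "Summary tables for the number of migraine/headache days, change from baseline and the percent change by 4, 12 and 24 week intervals", with similar tables for acute migraine medication days. Each table carries a treatment difference and an interval, described thus: "These confidence intervals will be based on normal approximation. Stratification will not be used for these intervals". No covariate is named.

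Three other provisions bear on the point:

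- **ANCOVA.** SAP 2.5 defines the primary model: "Treatment and the stratification variable: baseline migraine days (continuous covariate) will be the independent variables". Medication days get their own version: "change in acute migraine medication day endpoints will be tested using an ANCOVA model similar to the one used for the primary endpoints", with baseline medication days as covariate. SAP 3.4.1 takes the ANCOVA estimate and the "associated confidence intervals for Weeks 1-12"; no other period is named. Neither section names headache days as an ANCOVA outcome.
- **Repeated measures.** Later in SAP 3.4.1, change in migraine days "for the six, 4 week intervals from Weeks 1 to 24 will also be analyzed using repeated measures". The listed terms are treatment group, timepoint and continuous baseline migraine days. A difference and interval are promised at each timepoint.
- **Subgroups.** SAP 2.7.1 states: "A forest plot will also be created for subgroup analyses and will display treatment differences". SAP 3.4.1 adds that the plot covers Weeks 1-12 and shows an interval. Neither says how the difference or interval is computed.

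**The concern.** The sponsor already treats baseline migraine days as prognostic: randomization is stratified on it (SAP 1.3) and the primary model adjusts for it. The covariate costs nothing to obtain, because entry requires at least 25 of 28 baseline diary days (SAP 1.2). Yet adjustment stops at Weeks 1-12 for most outcomes.

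The primary objective concerns repeat doses. Weeks 1-12 are Days 0-83 (SAP Table 3) and the second infusion falls at Day 84 ± 3 (SAP Table 1), so the Weeks 1-12 estimate essentially describes one infusion. Information on later infusions comes from later intervals. A reader following the effect over time would set a baseline-adjusted figure for Weeks 1-12 beside raw differences for several later periods. Those raw differences have wider intervals than necessary and retain whatever chance baseline imbalance is present.

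**Working it through.** **1. What is covered.** Reading SAP 2.5 and 3.4.1 together:

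| Outcome and interval | Baseline-adjusted estimate planned? |
|---|---|
| Migraine days, Weeks 1-12 | Yes, ANCOVA |
| Migraine days, six 4-week intervals to Week 24 | Intended, repeated measures (see step 2) |
| Migraine days, pooled Weeks 13-24 and 1-24 | No |
| Migraine days, Weeks 25-48 (4-week parts, 25-36, 37-48, 25-48) | No |
| Medication days, Weeks 1-12 | Yes, ANCOVA |
| Medication days, all other intervals | No |
| Headache days | None named |
| Subgroup forest plot, Weeks 1-12 migraine days | Method not stated |

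**2. The repeated-measures terms.** With treatment, timepoint and baseline only, the treatment effect is one parameter shared by all six timepoints. The fitted difference is then identical at each. A separate difference at each timepoint needs a treatment-by-timepoint term, which is not listed.

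**3. The plan's own figure.** Inputs from SAP 1.5: 200 per group, difference 1 day, SD 2.7 or 3 days; two-sided 5% from SAP 2.5. The normal-approximation power is 95.9% at SD 2.7 and 91.5% at SD 3. The stated figures (at least 95%, and 90%) reproduce.

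**4. Unadjusted half-width.** Taking 2.7 as the SD of the change score (an assumption, since the plan does not say whether it is before or after adjustment):

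1.96 × 2.7 × √(2/200) = 0.53 day.

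**5. Gain under equal variances.** The documents give neither a baseline SD nor a baseline-to-post correlation ρ, so both are assumed. If baseline and post-treatment counts have the same variance σ², the change score has variance 2σ²(1 − ρ) and the ANCOVA residual has σ²(1 − ρ²). The ratio of standard errors is √((1 + ρ)/2).

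| ρ | SE ratio | Half-width (days) | SE reduction |
|---|---|---|---|
| 0.3 | 0.806 | 0.43 | 19% |
| 0.5 | 0.866 | 0.46 | 13% |
| 0.7 | 0.922 | 0.49 | 8% |

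**6. Gain under unequal variances.** Let b be the slope of post-treatment on baseline days and S the baseline SD. The adjusted variance is 2.7² − (b − 1)²S².

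- S = 3, b = 0.5: 7.29 − 0.25 × 9 = 5.04, SD 2.245, half-width 0.44, SE 17% smaller.
- S = 2, b = 0.5: 7.29 − 0.25 × 4 = 6.29, SD 2.508, half-width 0.49, SE 7% smaller.
- b = 0.9, S from 2 to 3: half-width about 0.53, SE less than 1% smaller.
- b = 1: no gain.

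**7. A smaller group, for illustration.** With 50 per arm (assumed), the unadjusted half-width is 1.96 × 2.7 × √(2/50) = 1.06 days. At ρ = 0.5 the adjusted value is 1.06 × 0.866 = 0.92.

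**The case against.** The strongest reply is that little depends on these intervals. Randomization keeps the raw differences unbiased, and stratification at 9 migraine days limits imbalance in that baseline. The primary and medication-day tests already use ANCOVA, the key secondary tests use stratified CMH, and none of the intervals at issue enters the testing sequence of SAP 2.7.5. SAP 2.5 promises only summary statistics with intervals for secondary endpoints. Weeks 25-56 are labelled a long-term safety period, and the sponsor is unblinded once the last subject completes Week 24. All of this stands, and it limits the point to an efficiency improvement.

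Three stronger readings are tempting and fail.

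- A reader might infer that everything after the second dose lacks an adjusted estimate. The repeated-measures model is meant to supply one for migraine days in Weeks 13-16, 17-20 and 21-24. It can be said that pooled Weeks 13-24 is just their average, but the SAP does not ask for that contrast.
- A reader might infer that the forest plot is unadjusted. The sentences on normal approximation concern the summary tables. The plot covers Weeks 1-12, where the ANCOVA also applies, so either reading is open. The defect is an unstated method.
- A reader might want a single figure for the gain. Without a baseline SD or correlation in the documents, only a range under stated assumptions is defensible, and it includes almost no gain.

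**Conclusion.** The point holds as a free improvement. No baseline-adjusted estimate is planned for headache days, for medication days in intervals other than Weeks 1-12, for migraine days in Weeks 25-48, or for the pooled Weeks 13-24 and 1-24 migraine-day averages. The repeated-measures model lacks the term needed for what it promises, and the forest plot needs a named method.

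The cost of leaving the text alone is precision in descriptive secondary intervals, not bias and not error control. At 200 per arm and a change-score SD of 2.7, the half-width of 0.53 day would become about 0.43 to 0.49 under equal variances and correlations of 0.3 to 0.7. Under unequal variances (baseline SD 2 to 3, slope 0.5 to 1) it would be 0.44 to 0.53. The coverage gaps follow directly from the text; the size of the gain rests on the assumed correlation, baseline SD and slope.

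**What to change.** Amend SAP 3.4.1 as follows:

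1. Take treatment differences and 95% confidence intervals for change from baseline in migraine, headache and acute migraine medication days, in every 4-, 12- and 24-week interval, from the Section 2.5 ANCOVA, with the corresponding baseline as a continuous covariate. Naming the matching baseline also settles a loose end: 3.4.1 describes the ANCOVA as controlling for baseline migraine days, whereas 2.5 uses baseline medication days for that endpoint.
2. Name the same model for the Weeks 1-12 subgroup forest plot, here and in 2.7.1.
3. Add treatment-by-timepoint to the repeated-measures model.
4. Keep the raw summaries, and retain the normal-approximation intervals for number of days and percent change. Deleting those two sentences outright would leave these intervals with no stated method.

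The cost is SAP wording and running the planned PROC MIXED code on more intervals. No new data are needed, subjects are unaffected, and the testing sequence is unchanged.
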